8.3. Exploratory Immunogenicity Analyses

Not applicable.

9. SAFETY EVALUATION

9.1. Demographic and Other Baseline Characteristics

Summaries of sex, ethnicity, race, baseline flavivirus immune status, age, and BMI will be presented by treatment group and overall ([Table 17](#) and [Table 18](#)). In accordance with NIH reporting policy, subjects may self-designate as belonging to more than one race or may refuse to identify a race, the latter reflected in the eCRF as “No” to each racial option.

9.1.1. Pre-Existing Medical Conditions

Pre-existing medical conditions will be summarized by MedDRA System Organ Class, treatment group and overall ([Table 19](#)). Individual subject listings will be presented for all demographics in [Listing 6](#).

9.1.2. Prior and Concomitant Medications

Prior and concomitant medications will be summarized by WHO Drug Level 1 and Level 2 Codes, treatment group, and overall ([Table 237](#)). Individual subject listings will be presented for all concomitant medications ([Listing 22](#)).

9.2. Measurements of Treatment Compliance

All subjects were to receive 2 doses of investigational product administered in the clinic. The number of doses of investigational product administered to subjects will be presented by enrollment group as part of the subject disposition table ([Table 11](#)).

A listing of subjects who discontinued dosing and the reason will be included in [Listing 2](#).

9.3. Adverse Events

When calculating the incidence of adverse events (i.e., on a per subject basis), each subject will only be counted once per AE using the event with maximum severity and any repetitions of adverse events within a subject will be ignored; the denominator will be the total treatment group size or the corresponding number of subjects receiving the second dose, as appropriate. All unsolicited adverse events reported will be included in [Listing 11](#).

An overall summary of adverse events from first administration of study vaccine to the end of the study is presented in [Table 36](#), [Table 37](#), and [Table 38](#) for all subjects, baseline flavivirus positive subjects and baseline flavivirus negative subjects, respectively.

9.3.1. Solicited Events and Symptoms

Statistical comparisons of the frequency and duration of vaccine related Grade 3 local, systemic, or laboratory AE, and Grade 2 or greater local or systemic reactogenicity are presented post dose 1, post dose 2, and post any dose in [Table 43](#), overall and by pre-vaccination flavivirus immune status. Frequencies of each adverse event are compared between dosage groups using Fisher’s Exact test. The distribution of the duration of adverse events (excluding laboratory AEs) will be compared between all dosage groups using the 2-samples Wilcoxon rank sum test.

The frequency and proportion of subjects experiencing any local or systemic solicited event over the 8-day post-vaccination reporting period will be summarized by dose number, pre-vaccination flavivirus immune status, severity and treatment group in [Table 44](#) (post dose 1, post dose 2, and post any dose).

The number, percentage, and exact 95% CI of subjects experiencing each solicited event over the 8-day post-vaccination reporting period, collected in-clinic pre-vaccination, post-vaccination and via memory aid, will be summarized by pre-vaccination flavivirus immune status, dose number and symptom in [Table 45](#) (all subjects), [Table 46](#) (baseline ZIKV seropositive subjects), [Table 47](#) (baseline ZIKV seronegative subjects), [Table 48](#) (baseline ZIKV seropositive and DENV seropositive subjects), [Table 49](#) (baseline ZIKV seropositive and DENV seronegative subjects), [Table 50](#) (baseline ZIKV seronegative and DENV seropositive subjects), and [Table 51](#) (baseline ZIKV seronegative and DENV seronegative subjects).

The frequency and proportion of subjects experiencing any mild, moderate, or severe solicited local or systemic reaction will be summarized by pre-vaccination flavivirus immune status, treatment group, dose number and reaction in [Table 52](#) (local; all subjects), [Table 53](#), (local; baseline ZIKV seropositive), [Table 54](#) (local; baseline ZIKV seronegative), [Table 55](#) (local; baseline ZIKV seropositive and DENV seropositive), [Table 56](#) (local; baseline ZIKV seropositive and DENV seronegative), [Table 57](#) (local; baseline ZIKV seronegative and DENV seropositive), [Table 58](#) (local; baseline ZIKV seronegative and DENV seronegative), [Table 59](#) (systemic; all subjects), [Table 60](#), (systemic; baseline ZIKV seropositive), [Table 61](#) (systemic; baseline ZIKV seronegative), [Table 62](#) (systemic; baseline ZIKV seropositive and DENV seropositive), [Table 63](#) (systemic; baseline ZIKV seropositive DENV seronegative), [Table 64](#) (systemic; baseline ZIKV seronegative and DENV seropositive), and [Table 65](#) (systemic; baseline ZIKV seronegative DENV seronegative).

The frequency and proportion of subjects experiencing a mild, moderate, or severe **local or systemic solicited reaction** will be summarized by baseline flavivirus immune status, treatment group, dose number, reaction, pre-dose, and by post-vaccination day in the following tables:

Table A: Severity of Solicited Local or Systemic Reactogenicity Events, by Post-Vaccination Day:

Baseline Flavivirus Immune Status	2.5 mcg ZIPIV			5 mcg ZIPIV			Placebo		
	Post-Dose 1	Post-Dose 2	Post Any Dose	Post-Dose 1	Post-Dose 2	Post Any Dose	Post-Dose 1	Post-Dose 2	Post Any Dose
All Subjects	Table 66	Table 67	Table 68	Table 69	Table 70	Table 71	Table 72	Table 73	Table 74
Baseline ZIKV Seropositive	Table 75	Table 76	Table 77	Table 78	Table 79	Table 80	Table 81	Table 82	Table 83
Baseline ZIKV Seronegative	Table 84	Table 85	Table 86	Table 87	Table 88	Table 89	Table 90	Table 91	Table 92
Baseline ZIKV Seropositive and DENV Seropositive	Table 93	Table 94	Table 95	Table 96	Table 97	Table 98	Table 99	Table 100	Table 101
Baseline ZIKV Seropositive and DENV Seronegative	Table 102	Table 103	Table 104	Table 105	Table 106	Table 107	Table 108	Table 109	Table 110

Baseline ZIKV Seronegative and DENV Seropositive	Table 111	Table 112	Table 113	Table 114	Table 115	Table 116	Table 117	Table 118	Table 119
Baseline ZIKV Seronegative and DENV Seronegative	Table 120	Table 121	Table 122	Table 123	Table 124	Table 125	Table 126	Table 127	Table 128

[Figure 46](#), [Figure 47](#), and [Figure 48](#) will summarize the solicited local adverse event data overall and by treatment group and display the maximum severity experience by each subject for each solicited event following any dose, post dose 1, and post dose 2, respectively. Similar summaries for solicited systemic events are presented in [Figure 49](#), [Figure 50](#), and [Figure 51](#).

[Figure 52](#), [Figure 53](#), and [Figure 54](#) will summarize the solicited local event data overall and by treatment group and display the maximum severity experienced by each subject pre-dose and each day post-dose, post any dose, post dose 1, and post dose 2, respectively. [Figure 55](#), [Figure 56](#), and [Figure 57](#) are similar summaries for solicited systemic event data.

A listing of systemic and local solicited events is provided in [Listing 9](#) and [Listing 10](#), respectively.

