## 11.4 Final Analysis Plan

The primary Clinical Study Report (CSR) will summarize all safety and protocol-specified humoral immunogenicity results, including all primary and secondary endpoint data, collected through Day 750. Given the urgency to obtain data in a timely manner, additional humoral and cellular immunogenicity assessments will be summarized in one or more addenda to the main CSR. Prior to the interim database lock, a formal Statistical Analysis Plan that specifies all planned analyses will be developed. In the following an abbreviated version of the planned primary and secondary analysis is provided.

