#### **11.4.2 Safety Analysis**

The number, percentage (observed rate), and exact two-sided 95% CI for subjects reporting each solicited injection site reaction and solicited systemic reaction within 7 days following vaccination will be summarized by treatment group for each vaccination as well as overall (following any vaccination). In addition, maximum severity and duration of local and systemic reactions will be determined for each subject and summarized by group following each vaccination (as well as overall) and the resulting number and percentage of subjects will be summarized by severity grade (none, mild, moderate, severe). The number and percentage of subjects overall and in each group with laboratory AEs or abnormal laboratory values from the time of first vaccination through 28 days after the last vaccination will be listed by study visit and by toxicity grade.

For formal group comparisons of local reactogenicity, subjects will be assigned to “none” and “mild, moderate or severe (Grade 1, 2 or 3)” severity groupings based on their maximum severity of any solicited injection site reaction following 7 days after any vaccination. Local “mild, moderate, or severe” rates for subjects receiving moderate dose ZPIV and subjects receiving high dose ZPIV will be compared using a Fisher’s Exact Test. In addition, rates for any severe (Grade 3) local, systemic or laboratory toxicity reaction following any vaccination will be compared between the groups using a Fisher’s Exact Test.

The occurrence of SAEs and AESIs (see [Section 9](#)) will be presented by relationship to study vaccination, number and percentage of subject as well as by MedDRA® same System Organ Class (SOC) and Preferred Term (PT) for each study group as well as combined across study groups. Related SAE rates will be compared between the groups using a Fisher’s Exact Test.

The proportion of subjects reporting at least one related unsolicited AE until the end of the study will be summarized by MedDRA SOC and PT. The number, percentage (observed rate) and exact two-sided 95% CI for subjects reporting a related unsolicited AE overall, by same SOC, and by PT will be summarized by group for each vaccination.

The number and percentage (observed rate) of subjects that withdrew or discontinued their vaccination series due to any reason will be tabulated. Withdrawal/discontinuation rates between dose groups will be compared using a Fisher’s Exact Test.

---

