1. PREFACE

This Statistical Analysis Plan (SAP) for DMID Protocol 16-0034, “*Phase I, Randomized, Double-blinded, Placebo-Controlled Dose De-escalation Study to Evaluate the Safety and Immunogenicity of Alum Adjuvanted Zika Virus Purified Inactivated Vaccine (ZPIV) Administered by the Intramuscular Route in adult Subjects Who Reside in a Flavivirus Endemic Area*

” describes and expands upon the statistical information presented in the protocol.

This document describes all planned analyses and provides reasons and justifications for these analyses. It also includes sample tables, listings, and figures planned for the final analyses. Regarding the final analyses and Clinical Study Report (CSR), this SAP follows the International Conference on Harmonisation of Technical Requirements for Registration of Pharmaceuticals for Human Use (ICH) Guidelines, as indicated in Topic E3 (Structure and Content of Clinical Study Reports), and more generally is consistent with Topic E8 (General Considerations for Clinical Trials) and Topic E9 (Statistical Principles for Clinical Trials). The structure and content of the SAP provides sufficient detail to meet the requirements identified by the FDA and ICH, while all work planned and reported for this SAP will follow internationally accepted guidelines published by the American Statistical Association and the Royal Statistical Society for statistical practice.

This document contains four sections: (1) a review of the study design, (2) general statistical considerations, (3) comprehensive statistical analysis methods for immunogenicity and safety outcomes, and (4) shells of proposed tables and data listings and mock figures. Within the table, figure, and listing mock-ups (Appendices 1, 2, and 3), references to CSR sections are included. Any deviation from this SAP will be described and justified in protocol amendments and/or in the CSR, as appropriate. The reader of this SAP is encouraged to also review the study protocol for details on conduct of the study and the operational aspects of clinical assessments.

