3.2. Endpoints

Primary Endpoints:

1. Frequency and severity of solicited injection site and systemic reactogenicity from time of study vaccine administration through Day 8 after each administration of study vaccine overall and by dosage group and pre-vaccination flavivirus immune status.
2. Frequency and severity of unsolicited vaccine-related adverse events (AE), including vaccine-related laboratory AE, from first administration of study vaccine until 28 days after the last vaccination overall and by dosage group and pre-vaccination flavivirus immune status.
3. Frequency, type, and duration of serious adverse events (SAE) and adverse events of special interest (AESI) considered related to study vaccine from the first administration of study vaccine until the end of the study overall, and by dosage group and pre-vaccination flavivirus immune status.
4. Frequency of new onset chronic medical conditions reported at any time from the first administration of study vaccine until the end of the study overall, and by dosage group and pre-vaccination flavivirus immune status.
5. Comparison of the frequency, type and duration of vaccine-related Grade 3 local, systemic, or laboratory AE, and Grade 2 or greater local or systemic reactogenicity through Day 8 after each

study vaccine administration between dosage groups and by pre-vaccination flavivirus immune status.

6. Comparison of study withdrawals and discontinuation of study vaccination due to any reason between dosage groups and by pre-vaccination flavivirus immune status.

Secondary Endpoints:

1. Frequency of seroconversion to ZIKV at each post-vaccination visit measured by ZIKV ELISA and neutralization assay in comparison with baseline samples (collected at Visit 00) overall, and by dosage group and pre-vaccination flavivirus immune status.
2. Per Visit GMT as measured by ZIKV ELISA and neutralization assay after each study vaccine administration and for each post-vaccination visit overall, and by dosage group and pre-vaccination flavivirus immune status.
3. Peak GMT as measured by ZIKV ELISA and neutralization assay after each vaccination and overall, and by dosage group and pre-vaccination flavivirus immune status.
4. Proportion of subjects with at least a 4-fold rise in ZIKV GMT as measured by ZIKV ELISA and neutralization assay at 4 weeks after each vaccination compared with baseline overall, and by dosage group and pre-vaccination flavivirus immune status.

Exploratory Endpoints:

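### The SAP carries over none of the four Fisher tests in Protocol 11.4.2 as written: the withdrawal test gains a placebo arm, the any-local and related-SAE tests are dropped, and the any-Grade-3 test is split by event; SAP Section 15 records none of this.

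*SAP*

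**What the plan says.** Protocol 11.4 introduces its analysis text with: "In the following an abbreviated version of the planned primary and secondary analysis is provided". Section 11.4.2 then names four Fisher exact tests:

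1. Any solicited local reaction, Grade 1 to 3 against none, after any vaccination. The contrast is explicit: "rates for subjects receiving moderate dose ZPIV and subjects receiving high dose ZPIV will be compared using a" Fisher test.
2. Any Grade 3 reaction as one composite: "rates for any severe (Grade 3) local, systemic or laboratory toxicity reaction following any vaccination will be compared between the groups". No restriction to related events is given.
3. Related SAEs: "Related SAE rates will be compared between the groups using a" Fisher test.
4. Withdrawal or discontinuation, again with an explicit contrast: "Withdrawal/discontinuation rates between dose groups will be compared using a" Fisher test.

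Tests 2 and 3 do not say which groups; dose groups is the natural reading.

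The SAP Preface states: "This document describes all planned analyses and provides reasons and justifications for these analyses". Its tests appear in two places. Section 9.3.1 and Table 43 compare vaccine-related Grade 3 AEs, and reactogenicity of Grade 2 or greater, between the two ZPIV doses: "Frequencies of each adverse event are compared between dosage groups using" Fisher's test. Section 7.1 and Table 12 compare withdrawals and discontinuations; footnote a of Table 12 describes a test across all three treatment groups. SAP 3.2 states primary endpoint 6 as: "Comparison of study withdrawals and discontinuation of study vaccination due to any reason between dosage groups". Section 15 lists four changes (enrolment, combined interim analyses, baseline flavivirus screening, the second exploratory endpoint). None concerns these tests.

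**The concern.** Primary objective 2 is to compare safety between dosage groups, and the four tests in 11.4.2 are the protocol's stated way of doing so. If the SAP is followed as written:

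- The Table 12 p-value answers whether three arms are alike, which is not the question in endpoint 6.
- A dose difference confined to Grade 1 local reactions gets no test, although the protocol planned one.
- The single composite Grade 3 comparison becomes a set of sparse event-level comparisons.
- The related-SAE comparison disappears.

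A reader of the final report who holds it against the protocol would find planned comparisons missing or altered, with no explanation.

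**Working it through.** **The plan's own figures.** The only power statements concern seeing at least one event, 1 − (1 − p)^n. For n=35, p=4.5% this gives 80.04%; for n=80, p=2.0% it gives 80.14%. Both match the stated 80%. No power is given for any Fisher test.

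**The tests side by side.**

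| Protocol 11.4.2 | SAP |
|---|---|
| Withdrawal, dose groups | Table 12: three groups including placebo, overall and by serostatus |
| Any local, Grade 1–3 against none, two doses | No test; rates with exact CIs in Tables 36 and 45 |
| Any Grade 3 local, systemic or laboratory | Table 43, event by event; no composite row |
| Related SAEs | No test; Table 36 (with exact CI) and Table 138 |

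**What Table 43 covers.** Its first block is limited to vaccine-related Grade 3 AEs. Its second block, Grade 2 or greater local or systemic reactogenicity, has no relatedness limit. A Grade 3 solicited reaction therefore enters a test whatever its attribution, pooled with Grade 2. Of the reactions in the protocol's composite, mainly unrelated Grade 3 laboratory AEs enter no test.

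**Inputs for the size.** 35 subjects on 2.5 mcg, 45 on 5 mcg (Protocol 11.2) and 5 + 5 = 10 on placebo (SAP 4.4.3). A two-sided 5% level and all event rates and counts below are assumptions; the documents give none for these tests.

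**Method.** The Fisher p-value sums the hypergeometric probabilities of all tables with the same margins that are no more probable than the observed one; the three-group version does the same over 35/45/10. Power is the binomial probability of all outcomes with p ≤ 0.05, by full enumeration. Example, 0/35 against 6/45: C(45,6)/C(80,6) = 0.0271 and C(35,6)/C(80,6) = 0.0054, so p = 0.0325. With 5/45 instead, 0.0508 + 0.0135 = 0.064.

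**Withdrawals, two-dose against three-group test.**

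| True rates 2.5 mcg / 5 mcg / placebo | Two-dose rejects | Three-group rejects | Tests disagree |
|---|---|---|---|
| 5 / 5 / 5% | 1.6% | 3.4% | 3.5% |
| 5 / 20 / 10% | 43% | 39% | 7.6% |
| 5 / 5 / 30% | 1.6% | 61% | 59% |

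Example counts: 0/35, 6/45, 1/10 give p=0.033 between doses and 0.067 across three groups; 1/35, 1/45, 3/10 give 1.0 and 0.009.

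**Any local reaction.** At 40% against 70% the protocol's test has 75% power. If that whole difference is Grade 1 and Grade 2 or greater is 5% in both doses, a Grade 2-or-greater row rejects 1.6% of the time.

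**Composite against single event.** One event at 5% against 12% has 11% power. A composite of six such events has 66% if they are independent, 46% to 30% at latent correlation 0.3 to 0.7 (Gaussian copula), and 11% if they overlap completely.

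**Related SAEs.** With 0/35, at least 6/45 are needed for p<0.05. Power is 2% at 0% against 5%, and 29% at 0% against 10%.

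**The case against.** The other side has substance.

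- The protocol calls its own text abbreviated and refers to the SAP for more. Of the primary endpoints, only 5 and 6 are worded as comparisons, and those are the two to which the SAP attaches p-values. Table 43 properly implements endpoint 5. This explains the SAP's choices, but referring to the SAP for additional information does not cover removing tests or changing a contrast unannounced. It also does not rescue Table 12, which departs from the SAP's own endpoint 6.
- Protocol 11.1 says the trial does not formally test hypotheses. True, but it adds that vaccine will be compared with placebo and dose levels with each other. A placebo comparison is legitimate; it is a different question from endpoint 6.
- A reader might infer that the Table 12 p-value is uninterpretable. It is not: n (%) for each arm is printed beside it.
- A reader might infer that Grade 3 events judged unrelated escape all testing, or that no combined Grade 3 rate is shown. Neither holds. Table 43's second block ignores attribution. Table 44 gives the Severe row for any local or systemic solicited event by arm, and Tables 195, 212 and 226 give maximum laboratory severity. Only the union with laboratory Grade 3 is not tabulated.
- The magnitudes rest on chosen rates. The 61% figure needs 30% placebo withdrawal, and the 75% figure a 30-point difference. This stands, and it limits the size of the point.

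**Conclusion.** The point holds at moderate weight. None of the four tests in Protocol 11.4.2 survives unchanged in the SAP: two are absent, one is split by event and one has a different contrast. None of the four departures is in Section 15. The clearest defect is Table 12, whose stated test does not address primary endpoint 6 and can give a different answer, though disagreement is uncommon (3.5% and 7.6% in the first two scenarios) unless placebo differs from both doses. The omitted any-local test matters mainly for a Grade 1 effect, and its rates remain visible by arm. Losing the composite Grade 3 test costs between nothing and a good deal of power, depending on an unknown correlation. Losing the related-SAE test costs little.

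Because this SAP cites a protocol version of December 2021, after both interim analyses (December 2018 and December 2020), a reader might infer that results prompted the changes. Nothing in the documents supports that. The defect is that the departures are unstated, in an exploratory trial with no multiplicity adjustment.

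**What to change.** 1. Table 12: make every p-value, overall and in each serostatus stratum, a Fisher test of 2.5 against 5 mcg. Keep placebo as a descriptive column.
2. Add the protocol's any-local test (Grade 1 to 3 against none, within 7 days, any dose, all subjects) between the two ZPIV doses, as a p-value on the any-local row of Table 45 or as a row in Table 43.
3. Add one row for any Grade 3 local, systemic or laboratory reaction regardless of relatedness, all subjects, post any dose, with the same Fisher test. Give it its own title, because Table 43 is titled as vaccine-related and through Day 8. Use the existing windows: solicited reactions through Day 8, laboratory results through 28 days after the last vaccination, so that the Day 15 draws count.
4. Either add the related-SAE test with a note on its very low power, or retire it with a reason in Section 15. Record any other deliberate departure from 11.4.2 there.

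The cost is a changed footnote, two rows, one extra table title or footnote, at most three new p-values and a short paragraph in Section 15. No new data are needed. The drawback is a few more unadjusted p-values, so the new rows should not be extended to single doses or serostatus strata.
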